An interim analysis will be conducted after at least 30 subjects reach Week 12 (complete 12 weeks of treatment) and complete the specified assessments for the Week 12 ESSDAI score. The interim analysis will be conducted in a fully blinded manner such that treatment group assignments of study subjects are not known and are not used in any manner in the analysis. A blinded examination of the variance of the primary endpoint will be performed and compared to the assumption used in planning the study. If this comparison suggests the initial assumption was substantially too low, the total study sample size may be increased by up to 45 additional subjects (ie, to a maximum of 120 subjects in total) to maintain adequate statistical power. The blinded IA will not interfere or alter any subject's treatment, that is, subjects who were enrolled before the IA is completed will continue the originally assigned treatment arm if they have received at least 1 treatment and the dose is considered safe.

Ongoing assessment of safety will be performed by an independent Data Monitoring Committee (DMC). The DMC may make recommendations to the Sponsor regarding conduct of the study based on safety observations.

Figure 1: Study Design Schematic

Duration of Study:

The approximate duration of the study is up to a 5-week screening period (35 days), a 12-week double-blind treatment period (84 days), and 6 weeks of follow-up (42 days), for a total of up to 23 weeks (161 days).

Number of Subjects:

Approximately 75 subjects will be randomized across the three arms of this study. The study will utilize an equal randomization scheme (1:1:1) that will result in approximately 25 subjects in each arm. An interim analysis will be conducted in a fully blinded manner to examine the variability of the primary outcome measure and compare that to the assumption used in planning the study. If this comparison suggests the initial assumption was substantially too low, the total study sample size may be increased by up to 45 additional subjects (ie, to a maximum of 120 subjects in total) to maintain adequate study power.

Study Population:

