The sample size calculation is based on the power to compare change from baseline in ESSDAI at Week 12 between active treatment arms (lulizumab or BMS-986142) and the placebo arm. With a two-sided, two-sample t-test at significance level 0.05, data from 25 treated subjects per arm will provide approximately 90% power to detect a placebo-adjusted 3-point decrease from baseline for each active treatment group, assuming common standard deviations of 3.2. In addition, the Hochberg’s step-up procedure will be used to adjust the multiplicity due to the comparison of two active treatment arms (lulizumab or BMS-986142) to the placebo arm.

The primary efficacy analysis will be conducted on all randomized subjects who received at least one dose of study drug.

An interim analysis will be conducted after at least 30 subjects reach Week 12 (complete 12 weeks of treatment) and complete the specified assessments for ESSDAI. The interim analysis will be conducted in a fully blinded manner such that treatment group assignments of study subjects are not known and are not used in any manner in the analysis. A blinded examination of the variance of the primary endpoint will be performed and compared to the assumption used in planning the study. If this comparison suggests the initial assumption was substantially too low, the total study sample size may be increased by up to 45 additional subjects (ie, to a maximum of 120 subjects in total) to maintain the desired study power. Regardless of the outcome from the blinded examination of variability, the study sample size will not be decreased. A maximum study sample size of 120 subjects in total, ie, 40 subjects per arm, can provide each active treatment arm 79% power to detect a placebo-adjusted 3-point decrease from baseline for common standard deviations as large as 4.8, using a two-sided two-sample t-test comparing each active treatment arm to placebo at significant level 0.05.

Endpoints:

The primary endpoint is to compare the change from baseline in ESSDAI score at Week 12 between active treatment arms (lulizumab or BMS-986142) and the placebo arm.

Secondary Endpoints:

- Change from baseline in ESSPRI score at Week 12
- Proportion of subjects with ≥ 3 points of improvement from baseline in ESSDAI at Week 12
- Proportion of subjects with ≥ 1 point of improvement from baseline in ESSPRI at Week 12

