8 STATISTICAL CONSIDERATIONS

8.1 Sample Size Determination

The sample size calculation is based on the power to compare change from baseline in ESSDAI at Week 12 between active treatment arms (lulizumab or BMS-986142) and the placebo arm. With a two-sided two-sample t-test at significance level 0.05, data from 25 treated subjects per arm will provide approximately 90% power to detect a placebo-adjusted 3-point decrease from

baseline for each active treatment group, assuming common standard deviations of 3.2.⁶⁶ In addition, the Hochberg's step-up procedure will be used to adjust the multiplicity due to the comparison of two active treatment arms (lulizumab or BMS-986142) to the placebo arm.

The primary efficacy analysis will be conducted on all randomized subjects who received at least one dose of study drug.

An interim analysis will be conducted after at least 30 subjects reach Week 12 (complete 12 weeks of treatment) and complete the specified assessments for ESSDAI. The interim analysis will be conducted in a fully blinded manner such that treatment group assignments of study subjects are not known and are not used in any manner in the analysis. A blinded examination of the variance of the primary endpoint will be performed and compared to the assumption used in planning the study. If this comparison suggests the initial assumption was substantially too low, the total study sample size may be increased by up to 45 additional subjects (ie, to a maximum of 120 subjects in total) to maintain adequate study power.^{67,68,69} Regardless of the outcome from the blinded examination of variability, the study sample size will not be decreased. A maximum study sample size of 120 subjects in total, ie, 40 subjects per arm, can provide each active treatment arm 79% power to detect a placebo-adjusted 3-point decrease from baseline for common standard deviations as large as 4.8, using a two-sided two-sample t-test comparing each active treatment arm to placebo at significant level 0.05.

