7.11 Interim Analyses

One interim analysis will be conducted when at least 30 subjects reach Week 12 (complete 12 weeks of treatment) and complete the specified assessments for the Week 12 ESSDAI score. The interim analysis will be conducted in a fully blinded manner such that treatment group assignments of study subjects are not known and are not used in any manner in the analysis. Specifically, a blinded examination of the variance of the primary endpoint will be performed and compared to the assumption used in planning the study. If this comparison suggests the initial assumption is substantially too low, the total study sample size may be increased by up to 45 additional subjects (i.e., to a maximum of 120 subjects in total) to maintain adequate study power.^{28 29 30} Regardless of the outcome from the blinded examination of variability, the study sample size will not be decreased.

The blinded examination of the variance will be based on the following assumptions:

- the placebo adjusted change from baseline at Week 12 for both active treatment arms (lulizumab or BMS-986142) will be 3 ESSDAI points
- the change from baseline at Week 12 will be the same for both active treatment arms.

The calculation of the blinded examination of the variance will include randomized subjects who received at least one dose of study drug with non missing ESSDAI assessment both for baseline and Week 12. Subjects will be considered for analysis if their Week 12 assessment occur while on double-blind study medication.

The estimate of the blinded examination of the variance $S_{blinded}^2$ will be computed using the formula mentioned by Kieser and Friede (2000)³⁶:

$$S_{blinded}^2 = S_{pooled}^2 - \frac{n}{n-1} \cdot \sum_{i=1}^3 (\mu_i - \bar{\mu})^2$$

where:

- S_{pooled}^2 is the variance of change from baseline at Week 12 in ESSDAI as calculated based on all subjects included in the interim analysis
- n is the number of subjects included in the interim analysis (across all treatment groups)
- μ_i is the assumed change from baseline at Week 12 for each of the 3 arms
- $\bar{\mu}$ is the assumed overall mean. For this calculation it is assumed to be average of μ_i across all treatment groups

Since μ_i and $\bar{\mu}$, the $\sum_{i=1}^3 (\mu_i - \bar{\mu})^2$ will be approximated by the term below:

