$$\begin{aligned} & \left(\xi_{Lulizumab} - \frac{\xi_{Lulizumab} + \xi_{BMS-986142} + \xi_{Placebo}}{3} \right)^2 + \\ & + \left(\xi_{BMS-986142} - \frac{\xi_{Lulizumab} + \xi_{BMS-986142} + \xi_{Placebo}}{3} \right)^2 + \\ & + \left(\xi_{Placebo} - \frac{\xi_{Lulizumab} + \xi_{BMS-986142} + \xi_{Placebo}}{3} \right)^2 \end{aligned}$$

where

$$\xi_{Lulizumab} = \xi_{BMS-986142} = 3 \text{ ESSDAI points and } \xi_{Placebo} = 0.$$

The common standard deviation will be estimated based on the estimate of the blinded examination of the variance.

The common standard deviation will be compared against the initial study assumptions for sample size estimation (see [section 5](#)). Would it be substantially larger than the initially planned, the sample size for the study will be re-estimated taking into consideration the maintenance of adequate power for the study (see [section 5](#)).

The final decision on sample size and power for this study will be made by BMS senior management.

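### The SAP's blinded variance formula subtracts three times the between-arm variance, so the interim SD is biased low and needed sample size increases will often be missed

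*SAP*

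**What the plan says.** Protocol section 8.1 plans 25 subjects per arm for about 90% power to detect a 3-point placebo-adjusted difference, "assuming common standard deviations of 3.2". The synopsis fixes equal allocation: "The study will utilize an equal randomization scheme (1:1:1"). Protocol section 8.5 provides one blinded interim once at least 30 subjects have Week 12 ESSDAI data. The total may then rise from 75 to at most 120, and it may not fall.

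SAP section 7.11 gives the estimator: "S_{blinded}^2 = S_{pooled}^2 - \frac{n}{n-1} \cdot \sum_{i=1}^3 (\mu_i - \bar{\mu})^2". The pooled term is the variance of the Week 12 change over all interim subjects taken together, and n "is the number of subjects included in the interim analysis (across all treatment groups"). The arm means come from the assumption that "the placebo adjusted change from baseline at Week 12 for both active treatment arms (lulizumab or BMS-986142) will be 3 ESSDAI points". The SAP then writes the sum out term by term with values 3, 3 and 0 and no weight on any arm. For the decision, "The common standard deviation will be compared against the initial study assumptions for sample size estimation". An increase follows if the SD is substantially above plan. The text supplied gives no numerical threshold, and the final decision rests with the sponsor's senior management.

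**The concern.** The subtraction is meant to remove the part of the one-sample variance that comes from the arms having different means. Each arm holds a third of the subjects, so each squared deviation should carry weight 1/3. The SAP gives each arm the weight of the whole sample.

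An estimate that is too low has a one-sided effect here, because the sample size can go up but not down. It cannot cause a needless increase, but it can hide a needed one. The re-estimation is the trial's only prespecified interim adaptation and exists to protect power. With this formula it would tend to report that the planning SD is adequate when it is not.

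**Working it through.** **Inputs.** Two-sided t-test at 0.05, 3-point difference, SD 3.2, 25 per arm, cap of 40 per arm (Protocol 8.1). Allocation 1:1:1 (Protocol synopsis). Interim n = 30, assumed means 3, 3, 0, and the formula (SAP 7.11).

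**The plan's own power figures.** The noncentral t distribution gives 90.1% for 25 per arm at SD 3.2, and 78.8% for 40 per arm at SD 4.8. Both agree with the stated 90% and 79%, so the fault lies in the interim formula alone.

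**What the one-sample variance contains.** With n subjects in total and nᵢ in arm i,

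E[S²pooled] = σ² + (1/(n−1)) · Σ nᵢ(μᵢ − μ̄)².

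With nᵢ = n/3 this becomes

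E[S²pooled] = σ² + (n/(3(n−1))) · Σ(μᵢ − μ̄)².

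The mean of 3, 3, 0 is 2, so Σ(μᵢ − μ̄)² = 1 + 1 + 4 = 6. At n = 30:

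- present in the pooled variance: 30/(3 × 29) × 6 = 2.07
- subtracted by the SAP: 30/29 × 6 = 6.21
- excess: 4.14

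The ratio is exactly 3 at any n. At n = 75 the two terms are 2.03 and 6.08. Reading n as the per-arm size does not repair the formula: 10/9 × 6 = 6.67.

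**Bias when the plan is exactly right (SD 3.2, 3-point effect in both arms).** Expected pooled variance is 10.24 + 2.07 = 12.31. The SAP estimate is 12.31 − 6.21 = 6.10, whose square root is 2.47. The corrected estimate is 12.31 − 2.07 = 10.24, or 3.20. Simulation of 200,000 interims gives the same means.

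**Where the SAP estimate reaches the planning SD.** σ² = 10.24 + 4.14 = 14.38, so σ = 3.79. At that SD, 25 per arm gives 78% power and 35 per arm are needed for 90%.

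**Expected SAP estimate by true SD** (n = 30, 3-point effect; the SAP SD is the square root of the expected variance):

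| True SD | Expected SAP SD | Per arm for 90%, true SD | Per arm for 90%, SAP SD | Chance estimate exceeds 3.2: SAP | Same, corrected |
|---|---|---|---|---|---|
| 3.5 | 2.85 | 30 | 20 | 26% | 69% |
| 3.8 | 3.21 | 35 | 26 | 47% | 84% |
| 4.0 | 3.44 | 39 | 29 | 61% | 90% |
| 4.5 | 4.01 | 49 | 39 | 85% | 98% |
| 4.8 | 4.35 | 55 | 46 | 92% | 99% |

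At true SD 4.0, 29 per arm gives 80% power, 39 gives 90%, and staying at 25 gives 74%.

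**Effect on final power under an assumed rule** (re-size to 90% power from the estimated SD, floor 25 and cap 40 per arm). At true SD 4.0, no increase follows in 40% of simulated interims with the SAP formula and in 10% with the corrected one. Average final power:

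| True SD | SAP formula | Corrected |
|---|---|---|
| 3.5 | 86% | 90% |
| 3.8 | 83% | 88% |
| 4.0 | 81% | 87% |
| 4.5 | 77% | 82% |
| 4.8 | 75% | 78% |

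**Negative estimates.** At SD 3.2 the SAP variance is negative in about 1% of interims with the 3-point effect and about 5% with no effect. The text supplied has no rule for this.

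**The case against.** The algebra was not disputed; the objections concern the size and weight of the error.

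- *The loss is smaller than the expected values suggest.* This stands. Comparing 29 with 39 per arm treats both estimators as free of sampling error. Averaged over simulated interims of 30 subjects, the formula costs about 3 to 6 points of power, not 10. The rest of the shortfall from 90% comes from sampling noise or the 120 cap.
- *The trigger and the 90% target are assumed.* This also stands. SAP 7.11 refers to its section 5, which is not in the supplied text, and the documents speak variously of adequate and desired power. With an assumed trigger of 3.84 (20% above plan) and true SD 4.0, no increase follows in 75% of interims with the SAP formula and still in 42% with the corrected one. The miss rate changes with the trigger; the direction does not.
- *The decision is discretionary.* True, but the SD put before the decision-makers is biased low under any trigger.
- *The harm is bounded.* The total cannot fall below 75, type I error is not at issue, and a large excess in SD is still mostly seen: at 4.8 the SAP estimate exceeds 3.2 in 92% of interims. The damage is greatest at true SDs of about 3.5 to 4.0, where 90% power could be restored within the cap.
- *A factor may have been lost when the PDF was read.* This is possible for the prefactor, but nothing points to it. The printed formula and the definition of n are consistent with each other, and the written-out sum carries no weight either.

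**Conclusion.** The formula is wrong as written. Under 1:1:1 allocation it subtracts exactly three times the between-arm component, 6.21 instead of 2.07 at n = 30. That result depends on no trigger, power target or outside source. When the 3-point effect is true, the variance estimate is low by 4.14; if the true SD is 3.2, the estimate centres on an SD of about 2.47. With no drug effect the SAP estimate is low by 6.21, and the corrected one is itself low by 2.07.

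The consequence is lost power. For true SDs of 3.5 to 4.0 the SAP estimate fails to exceed even 3.2 in 39% to 74% of interims, against 10% to 31% with the correct term. The average power loss of about 3 to 6 points rests on the assumed re-sizing rule, n = 30 and a true 3-point effect in both arms. The formula must be corrected before the interim is run.

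**What to change.** In SAP section 7.11, replace n/(n−1) by n/(3(n−1)), or write the subtracted term as (1/(n−1)) · Σ nᵢ(μᵢ − μ̄)² with planned arm sizes nᵢ = n/3. With the assumed means this is 2n/(n−1), or 2.07 at n = 30.

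The unadjusted one-sample variance is an alternative that needs no assumed effect, but it is conservative. With a true SD of 3.2 and the 3-point effect it gives √12.31 = 3.51, which implies 30 per arm instead of 25, or 15 more subjects.

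If SAP section 5 does not already do so, state the SD that triggers an increase and the power to be restored.

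The correction is one line in the SAP. It changes no data, no blinding and nothing for patients.

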8 CONVENTIONS

8.1 Time from first diagnosis of Sjogren's syndrome

The time from first diagnosis of Sjogren's syndrome of T1DM is calculated as the number of years from the diagnosis date to informed consent date:

$$(1 + \text{consent date} - \text{diagnosis date}) / 365.25.$$

If the date of diagnosis is partially missing, the following rules will take effect:

- Missing day, but month and year are present: the day will be imputed as the 15th day of the month.
- Missing day and month, but year is present: the day and month will be imputed as 30 June of the year (provided that the imputed date is less than the consent date).
- Missing year, but day and month are present: No imputations will occur, and the subject will be excluded from all related summaries.
- Missing day, month and year: No imputations will occur, and the subject will be excluded from all related summaries.
- If any such imputed date falls after the consent date, then the diagnosis date will be taken as equal to the consent date.

In cases that these dates are presented in listings, only the portion of the date of diagnosis actually observed, rather than imputed dates, will be displayed in listings.

8.2 Analysis Window for Longitudinal Assessments

8.2.1 Baseline Value

For each subject, the baseline value of a parameter is defined as the last assessment of that parameter on or prior to the date/time of the first dose of the double-blind study medication.

If time of measurement of a parameter or time of first dose are missing, then the baseline value is defined as the last assessment of that parameter on or prior to the date of the first dose of the double-blind study medication.

8.2.2 Longitudinal Assessments

Day 1 for the double-blind treatment period is the start date of double-blind treatment medication. The observation closest to the target day (and time where applicable) is the measurement used in the analysis for each scheduled visit.

The following visit windows will apply for all measurements in the double-blind treatment and follow-up periods:

Table 8.2.2-1: Visit Windows for Double-Blind Treatment Period

Visit	Target Day	Day Range
Day 8 (Week 1)	8	Post-baseline - 11*
Day 15 (Week 2)	15	12 - 18*
Day 22 (Week 3)	22	19 - 25*
Day 29 (Week 4)	29	26 - 32*
Day 36 (Week 5)	36	33 - 39*
Day 43 (Week 6)	43	40 - 46*
Day 50 (Week 7)	50	47 - 53*
Day 57 (Week 8)	57	54 - 60*

Table 8.2.2-1: Visit Windows for Double-Blind Treatment Period

Visit	Target Day	Day Range
Day 64 (Week 9)	64	61 - 67*
Day 71 (Week 10)	71	68 - 74*
Day 78 (Week 11)	78	75 - 81*
Day 85 (Week 12)	85	82 - 95*

* see section 8.3 for the definition of double-blind treatment period

Day 1 for the follow-up period is the day after the last day of double-blind treatment period (see [section 7.4.1](#) for definition of last day of double-blind treatment period). The observation closest to the target day (and time where applicable) is the measurement used in the analysis for each scheduled visit. Because of the definition of post double-blind treatment observations that may still fall in the double-blind period (see Section 8.3) the early days during the follow-up period may actually provide data that are still considered as occurring during double-blind period.

Table 8.2.2-2: Visit Windows for the Follow-Up Period

Visit	Target Day in Follow-up Period	Day Range in Follow-up Period
Day 106 (Week 15)	21	Post double-blind treatment - 31
Day 127 (Week 18)	42	32 - latest assessment

The use of post double-blind treatment observations that may still fall in the double-blind period is specified in Section 8.3.

For all parameters, if a subject has more than one measurement included within a window, the assessment closest to the target day will be used. In case of ties between observations located on different sides of the target day, the earlier assessment will be used. In case of ties located on the same side of the target day (i.e. more than one value for the same day but different time), the value with the earlier entry date/time will be used.

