- d Biopsy procedure window of ± 5 days (5 days **prior to dosing only** for Day 1/baseline biopsy)
- e Ophthalmologic procedure window of ± 5 days (5 days **prior to dosing only** for Day 1/baseline assessments), all assessments must be performed at same visit

In the event multiple assessments are required at the same study visit, the assessments should be performed in the following order whenever possible:

- 1) Disease activity assessments (eg, ESSDAI, ESSPRI, symptom scales)
- 2) Vital signs, physical exams, ECGs
- 3) Salivary flow assessments
- 4) Blood draws for safety labs, pre-dose PK assessments and biomarker assessments
- 5) Administration of study medication(s) and HCQ (if applicable)
- 6) Post-dose PK assessments (if applicable)
- 7) Ophthalmologic assessments (if performed on the same visit day)
- 8) Optional lip or parotid salivary gland biopsy

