5.4.2 Secondary Efficacy Assessments

5.4.2.1 Ophthalmologic Assessments

The following procedures should be performed at baseline/Day 1, Week 4, Week 8, and Week 12 by an ophthalmologist or optometrist experienced in the diagnosis and treatment of Sjögren's syndrome subjects and according to the methods described in Whitcher, et al.⁶⁵ A visit window of ± 5 days to perform the ophthalmologic assessments is acceptable (baseline/Day 1 assessment can be performed up to 5 days **prior to dosing** only), but all assessments must be performed during the same visit. The use of alternative ocular dyes may be permitted per local standards and/or regulations, and after consultation with the BMS Medical Monitor.

- Schirmer's test: The test (without anaesthesia) is performed by placing a narrow calibrated filter-paper strip in the inferior cul-de-sac of each eye. Aqueous tear production is measured by the length in millimeters that the strip wets during the 5 minute test period
- Tear break-up time (TBUT): Determined by instilling fluorescein dye and evaluating the stability of the pre-corneal tear film. After several blinks, the tear film is examined using a broad beam of the slit-lamp (biomicroscope) with a cobalt blue filter. The TBUT, defined as the time in seconds between the subjects's last blink and the first appearance of a random dry spot on the corneal surface, is measured 3 times and the mean value is recorded
- Ocular surface staining: The test is performed by instillation of fluorescein dye and either lissamine green or Rose bengal dye to stain the cornea and conjunctiva, respectively. After instilling the dye, the ocular surface is examined through a slit lamp (biomicroscope) the staining pattern is recorded per the method described in Whitcher, et al⁶⁵

The results from each of the above procedures will be recorded in site source records as well as entered into the corresponding eCRF provided by BMS or designee.

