7.5.2.2 Continuous Endpoints

The change from baseline in the following continuous endpoints will be analyzed with mixed effects model with repeated measures (MMRM) as described in [section 7.1.5.1](#). The model will

include all assessments for each parameters as defined in the protocol. Nominal p-values will be provided for those endpoints that are defined as secondary endpoints in the protocol.

- Change from baseline in ESSDAI scores at each time point of assessment. The change from baseline at Week 4, 8, are defined as secondary endpoints as per protocol. The change from baseline at Week 12 is the primary efficacy endpoint (see [section 7.5.1](#)). See [Section 8.6](#) for calculation of ESSDAI.
- Change from baseline in ESSDAI domain scores at each time point of assessment. This is considered as an exploratory efficacy endpoint. The scores for the ESSDAI domains Glandular, Articular, Hematological, Biological, Lymphadenopathy, Pulmonary and Constitutional will be analyzed with mixed effect models. The scores for the ESSDAI domains Central Nervous System (CNS), Cutaneous, Muscular, Peripheral Nervous System (PNS) and Renal will be analyzed with summary statistics. See [Section 8.6](#) for calculation of ESSDAI domain scores.
- Change from baseline in ESSPRI scores at each time point of assessment. The change from baseline at Week 4, 8, and, 12 are defined as secondary endpoints as per protocol. See [Section 0](#) for calculation of ESSPRI.
- Change from baseline in score of each individual ESSPRI components (Dryness, Fatigue, and Pain) at each time point of assessment. The change from baseline at Weeks 4, 8, and 12 are defined as secondary endpoints as per protocol. See [Section 0](#) for calculation of individual ESSPRI components.
- Change from baseline in mouth dryness as measured by unstimulated and stimulated salivary flow rate at Weeks 4, 8, and 12. See [Section 8.8](#) for calculation of salivary flow rate.
Change from baseline in eye dryness as measured by ocular surface staining (see [section 8.11](#)), Schirmer's test (see [section 8.9](#)), and tear break-up (see [section 8.10](#)) time test at Weeks 4, 8, and 12. These analysis will be repeated for each eye separately and combining information for the two eyes taking the average of test values on the same visit.

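### The SAP's weekly visit windows are narrower than the protocol's ±5-day eye-test window, so exams on 10 of 33 permitted days get a week label with no eye analysis

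*SAP*

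**What the plan says.** **Protocol.** Section 5.4.2.1 schedules Schirmer's test, tear break-up time and ocular surface staining at baseline and Weeks 4, 8 and 12, and adds: "A visit window of ± 5 days to perform the ophthalmologic assessments is acceptable". Footnote e to Table 5.1-2 repeats it: "Ophthalmologic procedure window of ± 5 days". Footnote a sets ±3 days for visits in general. The order-of-assessments list in 5.1 foresees that the eye exam may fall on another day than the main visit: "Ophthalmologic assessments (if performed on the same visit day".

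**SAP.** Section 8.2.2 introduces a single table: "The following visit windows will apply for all measurements in the double-blind treatment and follow-up periods". Its rows are contiguous weekly ranges. Weeks 4 and 8 run three days either side of target, and Week 12 runs from three days before to ten days after. No exception for eye tests is visible. Section 7.5.2.2 analyses the eye endpoints at three visits ("time test at Weeks 4, 8, and 12") and says the model will "include all assessments for each parameters as defined in the protocol". Section 8.3.1 says missing values are not imputed.

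The optional salivary gland biopsy has the same allowance in footnote d: "Biopsy procedure window of ± 5 days". SAP 7.9.2 links biopsy scores to visits by the visit windows, but cites Section 8.1 for them. Section 8.1 is about time since diagnosis; the windows are in 8.2.2.

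**The concern.** The analysis table fits the general ±3-day visit window but not the wider window that the protocol gives the eye tests. An exam done within protocol can therefore receive the label of a week in which no eye test is scheduled or analysed.

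The Week 12 row shows this most clearly. An exam on Day 95, ten days late and past the end of the permitted range (Day 90), counts as Week 12. An exam on Day 81, four days early and permitted, is labelled Week 11.

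The SAP does not say what the programmer should then do, and neither option is good:
- **Dropping the exam** loses protocol-compliant data.
- **Keeping it under its label** adds up to five sparse visit levels to a model with unstructured covariance (SAP 7.1.5.1). Three visits need 3 × 4 / 2 = 6 covariance parameters; eight need 8 × 9 / 2 = 36. Neither back-up model in 7.1.5.1 simplifies the covariance.

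Either way the reading does not count toward the Week 4, 8 or 12 value. At stake are some precision, and the reproducibility of three secondary endpoints.

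**Working it through.** The documents give no figure for this point, so there is none to reproduce. The check looks up every permitted day in Table 8.2.2-1.

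**Inputs.** Target Days 29, 57 and 85 and the weekly day ranges (SAP Table 8.2.2-1). Eye-test allowance ±5 days (protocol 5.4.2.1; Table 5.1-2 footnote e). General visit window ±3 days (footnote a).

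**Step 1: does the table fit the general visit window?** Target ±3 gives 3 × 7 = 21 days at Weeks 4, 8 and 12. All 21 fall in the right row. The same holds for ESSDAI visits within ±3 days at Weeks 2, 4, 6, 8, 10 and 12.

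**Step 2: does it fit the eye-test window?** Target ±5 gives 3 × 11 = 33 days.

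| Visit | Permitted days | SAP window | Permitted but labelled otherwise | Count |
|---|---|---|---|---|
| Week 4 | 24-34 | 26-32 | 24, 25 (Week 3); 33, 34 (Week 5) | 4 of 11 |
| Week 8 | 52-62 | 54-60 | 52, 53 (Week 7); 61, 62 (Week 9) | 4 of 11 |
| Week 12 | 80-90 | 82-95 | 80, 81 (Week 11) | 2 of 11 |

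Total: 4 + 4 + 2 = 10 of 33 days (30%). Baseline is not affected, because SAP 8.2.1 takes the last value on or before the first dose.

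**Step 3: does another SAP rule re-label these exams?** None that is visible.
- The closest-to-target rule at the end of 8.2.2 chooses among readings inside one window.
- Section 8.3 decides whether a reading belongs to the double-blind period, not which visit it belongs to.
- Section 8.3.1 rules out imputation.

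**Step 4: if the five days run from the actual visit.** The protocol does not name the reference point. If the visit itself may be three days off (an assumption), the span is ±8 days, or 3 × 17 = 51 days. Of these, 25 are mislabelled: 10 at Week 4, 10 at Week 8 and 5 at Week 12. Counting from the target day is the conservative reading.

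**Step 5: after correction.** With Days 24-34, 52-62 and 80-95, 0 of 33 days are mislabelled. On the ±8 reading those rows would still miss 6 + 6 + 3 = 15 of 51 days. Assignment to the nearest scheduled eye visit misses none, because the midpoints between targets (Days 43 and 71) lie outside Days 21-37, 49-65 and 77-93.

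**Biopsy.** Permitted Week 12 days are 80-90. Days 80 and 81 are labelled Week 11, so 2 of 11.

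**The case against.** **The governing text may be hidden.** SAP 7.5.2.2 refers to 8.9, 8.10 and 8.11 for these three tests, and those sections are not visible. An eye-specific window there would dispose of the point. This stands as a condition on the conclusion, although 8.2.2 as written covers every measurement and points to no exception.

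**Data loss is not demonstrated.** A reader might infer that these exams are discarded. The SAP does not say so; it only fixes their label. The opening of 8.2.2, which uses the observation nearest the target day for each scheduled visit, could also be read as assignment to the nearest scheduled eye visit. The table's explicit ranges for Weeks 3, 5, 7, 9 and 11 count against that reading. Likewise, the 7.5.2.2 sentence on including all assessments can mean all scheduled time points, so it is not a firm contradiction of 8.2.2.

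**The 30% is not a share of exams.** A reader might take it as three in ten readings lost, or assume an even spread and inflate the Week 4 and 8 standard errors by √(11/7) = 1.25. The documents give no exam dates and no ground for an even spread. Protocol 5.4.4 extends its assessor requirements to the eye procedures and asks that visits be scheduled around the assessor's availability, and 5.1 places the eye tests in the visit sequence. Both favour exams at the visit, within ±3 days, where nothing is mislabelled.

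**The biopsy adds little.** It is optional and only summarised descriptively.

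**Conclusion.** The mismatch is real and the day count is exact: measured from the target day, 10 of 33 permitted eye-test days carry a week label with no eye analysis. Exams on those days do not contribute to the Week 4, 8 or 12 eye estimates, whether they are dropped or kept as extra visit levels. This rests on two assumptions: that SAP 8.9-8.11 hold no eye-specific rule, and that the ±5 days run from the target day.

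The number of exams affected is unknown and may be zero. The endpoints concerned are secondary, with nominal unadjusted p-values. A reader might suspect that the primary analysis or the blinded sample-size re-estimation is affected too; neither is, because scheduled ESSDAI readings within ±3 days all map to the right visit. Severity: minor.

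**What to change.** Before unblinding, amend SAP 8.2.2 for Schirmer's test, tear break-up time and ocular surface staining only:
- Replace the weekly rows with Week 4 = Days 24-34, Week 8 = Days 52-62 and Week 12 = Days 80-95. The new rows must replace the weekly rows, not be added to them; otherwise Day 24, for example, would match both Week 3 and Week 4.
- State that the ±5 days run from the target day. If they are meant to run from the actual visit, assign each exam to the nearest scheduled eye visit instead.
- Say how eye readings outside these windows are handled.

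Optionally, use Days 80-95 for the Week 12 biopsy. Correct the cross-reference in SAP 7.9.2 from Section 8.1 to 8.2.2. Leave all ESSDAI windows unchanged.

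The cost is a few table rows and minor programming. One side effect is that an early-termination eye exam on any of the ten days would now count as Week 4, 8 or 12, at most five days from target. Over Days 2-81, the days that map to an analysed eye visit rise from 7 + 7 = 14 to 11 + 11 + 2 = 24.
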